- Pain variables: Pain assessments will be conducted using a digital algometer to obtain the threshold for discomfort caused by pressure. Pain assessment will also be measured by the subject rating his/her pain level (range 0 to 10, with 0 being no pain and 10 being the worst pain imaginable) during hand placement into an ice water bath (cold pressor test).
- Other data/specimens: Muscle/brain oxygenation will be measured using a near infrared spectroscopy sensor that will be secured to the skin. End-tidal carbon dioxide will be measured

via capnograph. Muscle sympathetic nerve activity will be measured using microneurography. Compensatory reserve index will be estimated by recording photoplethysmography signals from the finger. Body mass will be measured using a scale. Venous blood samples will be collected from a peripheral arm vein. Urine specific gravity, drug screening and a pregnancy test will be determined from a urine sample collected at the beginning of the visit.

Volume Collected

- Urine: 1 – 2 ounces collected at the beginning of each visit
- Blood: A maximum of 100 mL of blood will be collected during visits 2 and 3.

De-identified blood samples may be sent to the U.S. Army Institute of Surgical Research (USAISR) at Ft. Sam Houston, Texas. No subject information will be sent with the blood samples and no subject information will be exchanged with USAISR.

Chronological Detail

The times listed below are approximate and listed in order, from subject arrival.

All Specific Aims – 3 visits/subject (preliminary session: ~1 hour; 2 experimental visits: up to ~5.5 hours each; total time ~12 hours):

Visit 1 (preliminary visit) (~1 h)

- 60 min: consent form, HIPAA authorization, W-9 tax form, and self-reported medical history; resting blood pressure, 12 lead ECG, pregnancy test, if applicable, procedure familiarization, and drug screen; instruction sheet for experimental visits will be provided

Visits 2 and 3 (experimental visits) – 2 visits (~5.5 hours each visit)

- 15 min: urine sample (pregnancy test, if applicable), body mass measurement, instrumentation with ECG, blood pressure cuff
- 90 min: supine position assumed, insertion of an IV catheter in a vein of the arm, and muscle sympathetic nerve activity signal obtained
- 30 min: baseline data collection followed by pain assessments (cold pressor test and pressure algometry)

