- 45 min: drug administration (placebo or morphine) followed by progressive LBNP to the onset of syncopal signs/symptoms (blood pressure, cardiac output, forearm blood flow, cerebral blood flow, pulse oximeter, blood samples collected; heart rate, muscle sympathetic nerve activity measured continuously)
- Up to 60 min: recovery
- 30 min: pain assessments (cold pressor test and pressure algometry)
- Up to 60 min: recovery followed by pain assessments (cold pressor test and pressure algometry)

Primary Outcome Variables

The primary outcome variable will be the ability to tolerate the LBNP challenge prior to the onset of signs and symptoms associated with ensuing syncope.

Study Endpoints

Data collection will end when 30 subjects (15 male and 15 female) have completed the experimental protocol.

Sample Size Justification

No study has evaluated the effects of analgesics on LBNP tolerance in humans. The power and sample size estimates are based on findings from [name] laboratory showing reduced LBNP tolerance

Crandall_Morphine_Protocol_updated

Version <insert version number and date>

in the heat-stressed individuals (15). In that study heat stressed reduced LBNP tolerance by ~70% (997 cumulative stress index units to 303 cumulative stress index units; $P < 0.001$). Though we expect the analgesics to likewise reduce LBNP tolerance, we do not anticipate as large of a reduction as that observed with heat stress. Thus, the sample size calculation was based upon an anticipated reduction in LBNP tolerance of half that seen with heat stress, i.e., ~35% reduction in the cumulative stress index. Given this anticipated outcome, coupled with the associated variances observed in that study (15), we anticipate 15 subjects per drug trial will be sufficient to address the primary hypothesis that the administered analgesic reduces tolerance to a simulated hemorrhagic insult, with a study power=0.80 at an adjusted $\alpha=0.015$ to account for comparisons between drugs. That value was inflated to 30 subjects in total (15 male and 15 female) to permit a comparison in the primary responses between sexes for each of the administered drugs. That said, interim power analyses will be performed, with the number of required subjects adjusted based upon the variance of the obtained data.

5. Sub-Study Procedures:

Not applicable

6. Criteria for Inclusion of Subjects:

- 18-45 years of age
- Healthy
- Body mass index less than 35 kg/m²
- Body mass greater than or equal to 60 kg

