With regard to those outside the military, the experiments outlined in this application will determine the effect of currently employed pain medications on tolerance to a simulated hemorrhage in humans. These data will identify the pain medication that least compromises a human's ability to tolerate such an insult, thereby providing critical information to the pre-hospital medics on which pain medication should be employed for such an injury. Obtaining these data will be the first step in the continuum of research that will culminate in an increased understanding of the link between analgesia and hemorrhage. Moreover, the proposed work is particularly unique in that it will be the first investigation conducted in conscious humans to identify the optimal pain medication that will only minimally impair compensatory responses to a hemorrhagic injury, and thus the ability to "survive" that insult. This information will be valuable to both the military and civilian populations as it will improve pre-hospital care of the hemorrhaging victim.

14. Biostatistics:

The primary outcome variables are tolerance to the LBNP challenge with and without analgesic administration. The effects of morphine on LBNP tolerance, as well as pain assessment, will be evaluated via a paired T-test (i.e., placebo versus drug).

The effects of the administered drugs on hemodynamic and autonomic responses to each LBNP stage will be compared via two way mixed model ANOVA design, with main factors of drug and LBNP level (analyzed both by stage and by % completion of the entire LBNP protocol to pre-syncope). A significant interaction from those ANOVAs will be further explored via pairwise multiple comparison analyses.

Analysis assumptions will be carefully evaluated, data transformations considered, and Bonferroni-Hochberg will be used to adjust for multiple testing as appropriate.

15. References

1. Bellamy RF. The causes of death in conventional land warfare: implications for combat casualty care research. *Mil Med.* 1984 Feb;149(2):55-62.

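### The paired t-test for pain makes no stated use of the pre-drug pain test taken at each visit, so day-to-day variation in pain sensitivity stays in the error

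*Combined protocol and SAP*

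**What the plan says.** Under Chronological Detail, each experimental visit has a 30-minute block described as "baseline data collection followed by pain assessments (cold pressor test and pressure algometry"), placed before the drug. Every subject therefore has a pre-drug pain value on the placebo day and another on the morphine day.

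The later blocks run in this order:

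- dosing and the LBNP challenge, listed as "45 min: drug administration (placebo or morphine) followed by progressive LBNP to the onset of syncopal signs/symptoms"
- a first rest period, given as "Up to 60 min: recovery"
- a half-hour block for the first post-drug tests of both kinds
- a last block, which has to hold a second rest period as well as the second post-drug tests: "Up to 60 min: recovery followed by pain assessments (cold pressor test and pressure algometry")

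There are thus two post-drug pain assessments per visit. The list is introduced with the words "The times listed below are approximate and listed in order, from subject arrival", so nothing in it is tied to minutes after dosing.

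Section 14 (Biostatistics) covers pain in one clause: it, like LBNP tolerance, "as well as pain assessment, will be evaluated via a paired T-test" of placebo against drug. The section does not say whether the variable is the post-drug value or a change from the pre-drug value, which of the two post-drug tests is used, or whether the pre-drug value enters at all. The primary outcome is LBNP tolerance, not pain.

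**The concern.** The trial's purpose is to see what an analgesic dose of morphine does to LBNP tolerance. Section 11 says analgesia is expected at these doses, and the list of blood assays contains no morphine concentration. The pain tests are therefore the planned objective check that the exposure was analgesic in these subjects.

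Pairing removes stable differences between subjects. It does not remove a subject's shift in pain sensitivity from one visit day to the next. The pre-drug test at each visit measures that shift, because it is taken on the same day and before any drug. An analysis of post-drug values alone leaves the shift in the error term. A weak pain result would then be harder to read than it need be, although the information to sharpen it had been collected.

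**Working it through.** **Inputs.** Planned completers: n = 30 (Study Endpoints). Each completer has one pre-drug value per visit and a post-drug value at each of two time points per visit, for two pain measures. The documents give no standard deviation, correlation or expected effect for pain, so the correlation below is an assumption shown over a range.

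**Set-up.** For one pain measure and one post-drug time point, let D be the post-drug value at the morphine visit minus that at the placebo visit, and B the same difference for the pre-drug values. Let r be the correlation of D and B across subjects. B precedes the drug at both visits, so it cannot contain a drug effect from its own visit.

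**Three analyses, as variance of the estimated drug effect relative to a paired t-test on post-drug values:**

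1. Post-drug values only: 1.
2. Change from pre-drug value, D − B, if D and B have equal variance: 2(1 − r).
3. Regression of D on B, reading the effect at B = 0: (1 − r²) × [1 + 1/(n − 3)], with B treated as normal with mean zero. At n = 30 the last factor is 1 + 1/27 = 28/27 = 1.037, the average price of estimating one slope.

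| Assumed r | Change score | Adjusted | Equivalent n (30 / adjusted) |
|---|---|---|---|
| 0 | 2.00 | 1.04 | 29 |
| 0.3 | 1.40 | 0.91 × 1.037 = 0.94 | 32 |
| 0.5 | 1.00 | 0.75 × 1.037 = 0.78 | 39 |
| 0.7 | 0.60 | 0.51 × 1.037 = 0.53 | 57 |

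**Break-even.** Adjustment gains when 1 − r² < 27/28, that is r² > 1/28 = 0.036, or r above about 0.19. Below that it loses at most 3.7% in variance. A change score gains over post-drug values only when r exceeds 0.5, and it has larger variance than the adjusted analysis at every r in the table.

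**Timing, as a secondary check.** The plan's visit length reproduces first: 15 + 90 + 30 + 45 + 60 + 30 + 60 = 330 min = 5.5 h, which matches "Visits 2 and 3 (experimental visits) – 2 visits (~5.5 hours each visit"). It does so only with both capped blocks at 60 min and the second post-drug pain test inside the last of them.

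If the drug-and-LBNP block takes its full 45 min, the first post-drug test starts between 45 + 0 = 45 and 45 + 60 = 105 min after that block begins. The second can start from 45 + 30 = 75 min and must end by 45 + 60 + 30 + 60 = 195 min.

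To show what this could do, assume analgesia declines exponentially with a half-time of 2 to 4 h and the first test falls uniformly over 45–105 min. The effect at 105 min is then 0.5^(60/120) = 71% to 0.5^(60/240) = 84% of that at 45 min, and the average over the window is 85% to 92%. With an assumed standardised paired effect of 0.6 at 45 min, n = 30 and two-sided alpha 0.05, power is:

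- 0.89 if every test is at 45 min;
- 0.77 to 0.83 over the floating window;
- 0.61 to 0.76 if every test is fixed at 105 min.

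Nearly all the loss comes from testing later on average. The spread in times itself costs less than one percentage point.

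**The case against.** **Section 14 does not exclude a baseline.** A paired t-test on change from the pre-drug value would fit its wording. This stands: the documents do not show that the pre-drug test is ignored, only that no use of it is stated. Even on that reading the analysis is not the best available, since a change score has larger variance than post-drug values alone when r is below 0.5.

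**Pain is secondary.** It appears in neither Specific Aim and is not the primary outcome. This also stands, and it keeps the point minor.

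**A reader might infer something stronger from the schedule:** that floating test times bias or seriously dilute the morphine–placebo pain contrast, and that a fixed post-dose time is needed. The documents do not support that, for four reasons.

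- The recoveries are capped at 60 min. They have no minimum or fixed length, but they are not open-ended. A 120-min spread for the second test is too large, because that test sits inside its own capped block.
- Drug decline acts only on the morphine visit, so a gap between visits does not by itself cost effect. If LBNP ends earlier on morphine, as hypothesised, that visit's test moves closer to dosing.
- A common time late enough for every subject, about 105 min, would dilute the effect more than the floating window does under the same assumptions.
- A clock started at dosing would, if LBNP ends earlier on morphine, guarantee unequal time since pre-syncope at the two visits.

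What remains of the timing matter is that the plan permits variation and does not say that the times will be recorded.

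**Conclusion.** The point holds as a low-cost improvement to a secondary analysis. The plan collects a same-day, pre-drug pain value at each visit and states no use for it. Under the assumptions in the table, adjustment cuts the variance of the pain contrast by about 6% at r = 0.3, 22% at r = 0.5 and 47% at r = 0.7. The worst case is a loss of about 4%. The true r is unknown from the documents, so the gain is a range and not a prediction.

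The timing observation is only a reporting matter. The first test may start anywhere from about 45 to 105 min after the drug block begins, if that block takes 45 min. Whether this dilutes the contrast, and by how much, cannot be derived from the documents. Whether to anchor the test to dosing or to the end of LBNP is a design choice with costs either way. The LBNP tolerance comparison is unaffected by any of this.

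**What to change.** In Section 14, replace the plain paired t-test for pain with an analysis of the post-drug value adjusted for the same-visit pre-drug value. Do this separately for the cold pressor rating and the algometer threshold, and for each of the two post-drug time points.

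The simplest form regresses the paired post-drug difference on the paired pre-drug difference and reports the intercept with its confidence interval. The pre-drug difference should not be centred at its sample mean; if it is, the intercept is just the unadjusted difference. A within-subject model with subject as a fixed effect, visit condition and the pre-drug value gives the same estimate.

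Also record the actual start of each post-drug pain test, as minutes since dosing and minutes since the end of LBNP, and report both by visit. Section 11 refers to a first and a second administration, so the plan should say which one the dosing clock is counted from.

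The cost is a few sentences of text, one degree of freedom per analysis and a time stamp per test. No new measurement is needed, and the schedule, the care of subjects and the primary LBNP analysis do not change.

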We propose that if sufficient doses of commonly employed analgesics are administered to humans, otherwise appropriate cardiovascular responses to the hemorrhagic insult will be suppressed, thereby reducing the ability of the individual to tolerate that insult. That said, the effects of analgesic doses of such agents (i.e., doses that are recommended for the pre-hospital setting) on physiological responses necessary to preserve tolerance to a hemorrhagic insult in humans is entirely unknown. Moreover, the aforementioned guidelines by the CoTCCC for condition-specific analgesics are not based upon hypothesis driven scientific evidence in humans, but rather primarily from fully anesthetized animals. Thus, the applicability of that research to a soldier experiencing a hemorrhagic injury is questionable and remains a significant gap in the knowledgebase.

3. Concise Summary of Project:

Three separate protocols, one for each analgesic—fentanyl, morphine, and ketamine will be employed.

Three laboratory visits will be required for this protocol.

The first visit will begin with the consenting process. Should the interested subject qualify and agree to participate in the study, he/she will undergo two separate experimental visits (placebo and morphine) each conducted on a different day. The protocol for each experimental visit is identical. After instrumentation, subjects will rest quietly followed by baseline data collection and then assessments of pain (via algometer and the cold pressor test). Subjects will then receive the drug along with the progressive lower-body negative pressure (LBNP). This will be followed by a recording of post-drug data and re-performance of the pain assessments. For the placebo trial, saline (sodium chloride 0.9% or if unavailable, 5% dextrose in water) will be administered where “Drug Administration” is indicated above. The enrolled subject will be required to complete both placebo and morphine conditions.

- End tidal carbon dioxide: capnography
- Oxygen saturation: pulse oximetry
- Muscle and brain oxygen saturation: near infrared spectroscopy
- Compensatory reserve index: photoplethysmography of finger blood flow
- Body mass
- Venous catheter and blood samples: see list below
- Saline infusion (via venous catheter)
- Subjective pain reporting to pain assessments (cold pressor test)
- Threshold for pressure discomfort: digital algometer
- Urine specific gravity
- Drug screening
- Pregnancy test

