Morphine is a naturally occurring opiate. In addition to being a mu-opioid receptor agonist, it is also an agonist at the kappa-opioid receptors and delta-opioid receptors. Morphine has a set of common side effects that occur infrequently including diarrhea, nausea, vomiting, constipation, dry mouth, somnolence, confusion, weakness, sweating, hallucinations, dyspnea, apnea, hypoventilation, and urinary retention. Morphine tends to have more sedation than other opiates. Morphine has a therapeutic index of 70. This drug exposes you to the risks of addiction, abuse, and misuse. Respiratory depression is the most serious risk when administering with morphine. Naloxone will completely reverse all opioid effects within 2 minutes IV, 5 minutes IM, and 8 minutes intranasal administrations. This provides several routes of administration as a safety backup should IV access be lost. However, at the dose and time in the study proposed, we do not expect that significant respiratory depression will occur. We will monitor the patient's vital signs continuously. We will monitor pulse oximetry and end tidal carbon dioxide continuously. These two monitors will provide sufficient accuracy and robustness to administer this medication safely. An anesthesiologist will be present at all times to observe and intervene should the patient should the slightest evidence of respiratory depression well before any patient danger should arise. All standard airway intervention equipment will be readily available at all times.

Microneurography: There is a slight risk of a temporary pins and needles sensation or increased sensitivity to touch in the leg or arm during and following the test; however this feeling goes away within 2 to 7 days. This sensation may be similar to what is felt after jogging. A few subjects have noted some tiredness, soreness, or tingling in their muscles up to one week after the study.

Cold pressor test: This widely used technique for pain assessment presents minimal risk. For this test, immersion of the hand in ice cold water will elicit painful sensations as well as an increase in blood pressure. These typical responses are immediately lessened to pretest levels with the removal of the subject's hand from the ice water. The maximum duration for this test is three minutes and the subject can voluntarily remove the hand from the ice water at any time.

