Pressure algometry: This pain assessment technique is conducted by applying the rubber tip of a hand-held digital algometer on the subject's digit. Force will be gradually increased and the peak force is recorded when the subject first reports a painful sensation. Removal of the pressure from the algometer immediately relieves the painful sensation and the subject can voluntarily stop the test at any time.

Electrocardiogram: In some cases, individuals have developed a rash or redness where the patches were attached. This rash is mild and typically resolves without treatment.

Lower body negative pressure: The possible risks of this procedure are light-headedness, feeling faint, nausea and rarely a subject may faint. If this occurs, the procedure will stopped and the subject will begin to feel better almost immediately.

Loss of confidentiality: Anytime information is collected there is a potential risk for loss of confidentiality. Every effort will be made to keep information confidential, however, this cannot be guaranteed.

All other procedures (blood pressure, cardiac output, stroke volume, skin temperature, forearm blood flow, cerebral blood flow, skin blood flow, compensatory reserve index, end tidal carbon dioxide, oxygen saturation, muscle and brain oxygen saturation, body mass, urine specific gravity, drug screening, and pregnancy test) have little or no risk involved.

Overall, it is our opinion that the benefits derived from the proposed studies far outweigh the risks. The researchers are experienced with all procedures outlined in this study. A critical care trained RN will monitor the well-being of each subject and will be available as needed. Moreover, [name] (a board certified anesthesiologist) will oversee the administration of the analgesics and will continuously monitor the subjects throughout the protocol. [name] has specialized training in Pain Medicine, which includes the administration of the assessed drugs in his clinical practice; thus, he is well versed in the administration of these drugs and any potential adverse effects. In addition, [name], Medical Director of the Institute for Exercise and Environmental Medicine, or cardiology fellows currently working at the Institute for Exercise and Environmental Medicine, will be available to assist as needed.

11. Subject Safety and Data Monitoring:

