The doses of the drugs are expected to cause analgesia, but with the subject remaining conscious and responsive to verbal commands. These drugs are routinely administered for pain control in the absence of significant sedation. Nevertheless, if after the first or second administration of the selected analgesic the subject is not responding appropriately to verbal commands (e.g., is excessively sleepy/sedated) or experiences any related adverse responses to the administered drug, the trial will be cancelled for that subject.

Subjects who, during the study, manifest a new onset, previously hidden or unknown cardiovascular, neurological or metabolic disease/illness will be removed from the study.

The study will be stopped immediately for safety if a serious, unexpected problem or adverse event occurs. The entire project will be terminated if this event is determined to place future participants at undue risk.

12. Procedures to Maintain Confidentiality:

- 1) Information will be given to the principal investigator and his staff only.
- 2) Information concerning subject's medical histories will be furnished by the subjects to the staff.
- 3) This information will be used to determine qualification for participation in the investigation.
- 4) Personal information will remain in the subject's study chart and will not be released in any form to others unless permitted by the subject.
- 5) The consenting process for each subject will be conducted in a private room.
- 6) No subject will be identified by name or initials outside the laboratory records. All computer records will be coded and will not include the subject's name. All coded computer records will be saved on password protected computer systems and data files are maintained on a secure server.
- 7) The signed consent form will be kept on file in the subject's laboratory chart. Paper records of experiments and copies of executed consent forms will be locked in cabinets located in the research nurse's office which is locked whenever the nurse is not present.
- 8) The urine specimens collected for the drug screening will not be labeled and will be directly handed to a member of the study team by the participant (making it anonymous). There is no processing required as the results appear on the side of the specimen collection cup.

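### Does nausea during a morphine-day LBNP run leave the primary comparison undefined?

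*Combined protocol and SAP*

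**What the plan says.** **Endpoint.** Primary Outcome Variables defines the outcome as "the ability to tolerate the LBNP challenge prior to the onset of signs and symptoms associated with ensuing syncope". Chronological Detail describes the session as "drug administration (placebo or morphine) followed by progressive LBNP to the onset of syncopal signs/symptoms". Section 14 calls the end of the LBNP protocol pre-syncope and compares tolerance on the two days with a paired t-test.

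**LBNP risks (Section 10).** "The possible risks of this procedure are light-headedness, feeling faint, nausea and rarely a subject may faint". The next sentence reads: "If this occurs, the procedure will stopped and the subject will begin to feel better almost immediately".

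**Morphine risks (Section 10).** "Morphine has a set of common side effects that occur infrequently including diarrhea, nausea, vomiting, constipation, dry mouth, somnolence", and others.

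**Cancellation (Section 11).** The condition opens "if after the first or second administration of the selected analgesic the subject is not responding appropriately to verbal commands" and goes on to cover a subject who "experiences any related adverse responses to the administered drug, the trial will be cancelled for that subject".

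**Who is analysed.** Section 3 requires each enrolled subject to complete both conditions. Study Endpoints and Section 8 continue accrual until 30 subjects, 15 of each sex, have complete data.

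**The concern.** Nausea is on both risk lists. If it occurs during LBNP on a morphine day, one reading ends the run and takes the point reached as the tolerance value. The other cancels the trial for that subject, who is then replaced by another completer. On a saline day there is no drug reaction, so only the first reading is available. The asymmetry falls on the very contrast that the paired t-test estimates.

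The error could go either way. Counting a run stopped by nausea that has nothing to do with blood pressure would overstate the loss of tolerance. Cancelling a subject who truly reached pre-syncope early on morphine would understate it. The Sample Size Justification says no earlier study has measured this effect in humans, so the planned 35% loss is a conjecture. Aim 2 is about which drug costs least tolerance, so the size of the loss matters as well as the test result.

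**Working it through.** **1. The two rules side by side.** The endpoint needs signs or symptoms of impending syncope. The cancellation needs a reaction related to the drug. Each is tied to a cause, and nausea is not named as an endpoint in either place. The link from nausea to a tolerance value runs through a risk paragraph, where the stopping sentence directly follows the mention of fainting and may refer to fainting alone. Section 3 describes drug and LBNP as given together, while Chronological Detail puts the drug first. Which timing is meant is not for this review to settle. If the Section 11 check is made before LBNP starts, the overlap disappears.

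**2. The plan's own figure.** Planned loss: 0.35 × 997 = 349 CSI units, so the planned morphine mean is 997 − 349 = 648. The plan states n = 15, power 0.80, alpha 0.015. The SD of the paired difference is not given, so n = 15 cannot be reproduced, only inverted. Setting noncentral-t power at n = 15 and a difference of 349 equal to 0.80 gives SD = 368 (two-sided) or 410 (one-sided). At n = 30 with SD 368, SE = 368/√30 = 67 and power is 0.994.

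**3. Shift per disputed run.** Let L be the mean loss in the other pairs. A counted run stopped at S contributes 997 − S; a replacement contributes L on average. The mean therefore moves by (997 − S − L)/30. S is not in the plan; 303, the heat-stress level in the Sample Size Justification, serves as an example and 0 as the extreme.

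| L | S = 303 | S = 0 |
|---|---|---|
| 0 | 694/30 = 23.1 | 997/30 = 33.2 |
| 100 | 594/30 = 19.8 | 897/30 = 29.9 |
| 200 | 494/30 = 16.5 | 797/30 = 26.6 |
| 349 | 345/30 = 11.5 | 648/30 = 21.6 |

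At the planned loss, 11.5/349 = 3.3% of the effect and 11.5/67 = 0.17 of a standard error. If the run stops at 648 and L = 349, the shift is zero.

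**4. Chance of a significant loss.** Simulation with 40,000 trials per cell, n = 30, two-sided alpha 0.015, significance counted in the direction of loss, S = 303. The column with 0 counted runs is cancel-and-replace.

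| SD | L | 0 counted | 1 | 2 | 3 |
|---|---|---|---|---|---|
| 368 | 0 | 0.008 | 0.013 | 0.021 | 0.034 |
| 368 | 100 | 0.15 | 0.20 | 0.26 | 0.33 |
| 368 | 200 | 0.65 | 0.71 | 0.76 | 0.81 |
| 368 | 349 | 0.994 | 0.995 | 0.997 | 0.998 |
| 410 | 100 | 0.12 | 0.16 | 0.21 | 0.26 |

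Within the same trial (SD 368, L = 100, three events), the counted version is significant and the replaced version is not in 17.0% of trials. Merely drawing two different sets of ordinary replacements gives 4.3%. For one event the figures are 5.0% and 2.4%.

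**5. Heavier assumptions.** Take 3 to 9 of 30 subjects affected, runs cut to 25–75% of the value otherwise reached, true loss 347 (half of 997 − 303) and SD 366. Counting gives a mean loss of about 363 to 493, against 347 under replacement. With no true loss, the rate of declaring one runs from 1.6% to 43% when runs are counted and is about 0.7% under replacement. If nine subjects are cancelled and not replaced, power at the planned loss is still about 0.94.

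**The case for a change.** The strongest case for acting is that a relatedness test is only as good as its criterion, and Section 11 states none. Section 14 is silent on cancelled or symptom-stopped runs, and whoever judges the cause may know which day it is. The level and reason must be recorded at the time. If morphine's true effect is modest, two or three runs can move the answer (0.15 to 0.33 at L = 100). The 43% figure shows how far this could go if nausea were common.

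Part of this stands: Section 14 does not write the rule down, and the small-effect figures are correct under their assumptions. The rest is weaker.

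- Section 8 refers to a Section 4 on study procedures, and Section 3 to a drug-administration diagram; neither is visible in the public text. Symptom lists, dose timing, masking and repeat visits would normally be set out there, so their absence from the plan cannot be asserted.
- An index that accumulates over the run cannot be computed without the level and time reached. Beat-by-beat blood pressure is recorded, so a stop with falling pressure can be told from one without. Section 11 has an anesthesiologist in continuous attendance and already tracks withdrawals and adverse-event patterns.
- The 43% needs nine of 30 subjects stopped at a quarter of their usual tolerance. Section 10 describes morphine's side effects as infrequent, and a pattern on that scale would be plain to anyone analysing 30 pairs.
- Section 14 of this protocol specifies no between-drug test. Fentanyl and ketamine have separate protocols, so an effect on the Aim 2 ranking cannot be shown from these documents.

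**Conclusion.** No change to the plan follows. This is a gap in detail that analysts can fill sensibly: a run that ends in pre-syncope gives a value, and a run abandoned for a drug reaction leaves an incomplete pair outside the 30 completers. The documents do not contradict themselves on this point; individual cases may call for a judgement of cause. Either coding would be defensible.

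At the planned loss, each disputed run is worth 11.5 CSI units (3.3%, or 0.17 of a standard error), 21.6 at the extreme, and the test is unaffected. It would matter only if the true loss were well below plan and several such runs occurred. The documents give no event rate, and with no such run the two codings give the same result.

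These sizes rest on a back-solved SD of 368 (410 one-sided), 30 pairs, an illustrative stopping level of 303, and assumed event counts. The reading of the rules rests on the visible text, and the fuller procedures section may already settle the point.
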